Volunteers who: respond to advertisement i) using the online screening questionnaire relating to the inclusion/exclusion criteria (primarily whether they have sustained a medically diagnosed concussion within the last 14 days); ii) the study phone; iii) the study email, or who are referred by a health practitioner will be contacted by the study SC. The SC will further screen them for inclusion and exclusion criteria. If eligible to participate in the screening session participants will be forwarded an electronic participant information sheet and consent form and scheduled for the screening session. Individuals contacting the SC in response to advertising who meet exclusion criteria at any stage of the screening process will be provided with names and contact details of primary health services for concussion in Dunedin for follow up if desired. Those recruited via advertisement will be requested to obtain written confirmation of their concussion from their treating physician.

Inclusion criteria: Adults aged 18-60 years, biological sex: male, female, who have sustained a medically diagnosed concussion (mild Traumatic Brain Injury) based on published diagnostic criteria [13-15] and are not more than 14 days since injury [14].

Exclusion criteria: Individuals with past or current history of:

- Moderate to severe TBI as defined by published diagnostic criteria [16]
- Diagnosed concussion with associated trauma related abnormalities apparent on CT or MRI and/ or cervical spine fracture
- Diagnosed concussion due to assault
- Neck pain unrelated to concussion injury(/ies) (requiring treatment)
- Headache disorders (including cervicogenic, migraine (chronic), and tensions type headaches)
- Vestibular, oculomotor, neurological disorders
- Major psychiatric disorders currently being actively treated
- Physical injury that would prevent completion of the screening session

Study power:

Based on previously identified rates of neck impairment post-concussion [9, 17] it is anticipated that screening of **160** participants will be required to identify **60** individuals who meet inclusion criteria. Allowing for 50% of individuals to decline participation in the trial and a 10% drop-out rate, it is anticipated that data from **n=27** participants (treatment commenced with **n=30**) will be collected at all data collection time points. This group size is consistent with those currently used in randomised control trials investigating outcome following OMT of the

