Clinical data will be entered directly into the study's online data recording form which only the PI, SC and members of the research team will be able to access. Data in this form will be stored under a unique identifier generated during the initial screening session with the SC. Where raw data requires further analysis, it will be deidentified (VR and VNG outcomes) and routinely uploaded to the PIs (OG) password protected laptop or the password protected study laptop. Data collected using VR and VNG will be collected on the devices using the participants unique identifier.

Statistical Analysis

Descriptive analyses will be performed on sociodemographic data. Exploration of central tendency of all data will be evaluated using Kolmogorov-Smirnov and Shapiro-Wilk tests. Where data is significantly skewed, attempts will be made to transform using suggested methods [57]. Individual demographic variables (sex, age, BMI, IPAQ score) which could reasonably be expected to influence quantitative outcomes will be analysed for significance using univariate linear regression and included in models.

Objective 1:

Quantified feasibility outcomes: activity, compliance, and adverse event monitoring

- a. Descriptive statistics will be used for recruitment frequency and the number of eligible participants, the drop-out rate, and degree of missing data for the patient rated and clinical outcomes measures. The programme will be considered feasible if 80% of patients complete the programme until formal discharge based on the physiotherapists' assessment and treatment documentation.
- b. Adherence to the intervention by auditing and summarising patients' logbooks and the physiotherapists' assessment and treatment documentation. The SC will audit the documentation. Adherence will be considered acceptable if 80% of exercises had been recorded in the patient's logbooks.
- c. Adverse events from the treatment will be determined by auditing the physiotherapists' assessment and treatment documentation as well as inclusion of formal reports submitted to the study or HEC in the event of serious adverse events. Number of events will be considered.
- d. Patient satisfaction score (/12) from the patient satisfaction exiting questionnaire will be calculated and mean and 95% CI will be reported.

Triangulation of qualitative (analysis described above) and quantitative outcomes [79] will determine overall feasibility of using the SPE to inform treatment management.

Objective 2:

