Linear mixed method analysis of repeated experimental outcomes will determine treatment effect. Effect modifiers including sex and age as well as statistically significant demographic confounders will be included in the final model. Further secondary analysis may be undertaken using data collected at all time points. Multivariable linear regression will identify items of the VOMS which best predict VNG OM.

Data storage:

All data (including patient and health practitioner data) will be stored on the personal password-protected laptops of the PI ([name]) and or the password-protected study laptop. Any hard copies of the questionnaires and consent forms will be stored in the PI's office in a secure filing cabinet. Only the researchers mentioned in the application and the SC (tba) responsible for processing and analysis will have access to the de-identified data collected during the study. The principal researcher ([name]) and the SC will keep a list identification codes with participant names, so that participants can be identified by their coded data if needed.

A standardised hard copy of the summary report of the participants findings from the screening session completed by the SC will be provided to the treating physiotherapist (via postal mail). This will not be de-identified since it will be used by the treating physiotherapist to inform treatment. A copy of these reports will be kept on the PI's personal password-protected laptop.

The treating physiotherapist will record the clinical assessment and treatments, as required, on their usual practice management systems as well as information related to study feasibility.

All data will be stored for the duration of the study on the primary investigator's password-protected University laptop and will be accessible by members of the research team. It will also be stored for at least 10 years in the school's archive folder on the High-Capacity Storage System (HCSS). Any personal information held about the participants (such as contact details and hard copy questionnaires) may be destroyed at completion of the research. Coded study information may be kept by the University of Otago in secure, cloud-based storage indefinitely. All storage will comply with NZ I data security guidelines.

Potential problems: (medical/legal; issues with disclosure; conflict of interest, etc)

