If one section is missed or not applicable the score is calculated: 16 (total scored)
45 (total possible score) $\times 100 = 35.5\%$

Minimum Detectable Change (90% confidence): 5 points or 10 %points

NDI developed by: Vernon, H. & Mior, S. (1991). The Neck Disability Index: A study of reliability and validity. *Journal of Manipulative and Physiological Therapeutics*, 14, 409-415

(iii) *Dizziness Handicap Inventory (DHI)*

The Dizziness Handicap Inventory (DHI)

P1. Does looking up increase your problem?	 Yes  Sometimes  No
E2. Because of your problem, do you feel frustrated?	 Yes  Sometimes  No
F3. Because of your problem, do you restrict your travel for business or recreation?	 Yes  Sometimes  No
P4. Does walking down the aisle of a supermarket increase your problems?	 Yes  Sometimes  No
F5. Because of your problem, do you have difficulty getting into or out of bed?	 Yes  Sometimes  No
F6. Does your problem significantly restrict your participation in social activities, such as going out to dinner, going to the movies, dancing, or going to parties?	 Yes  Sometimes  No
F7. Because of your problem, do you have difficulty reading?	 Yes  Sometimes  No
P8. Does performing more ambitious activities such as sports, dancing, household chores (sweeping or putting dishes away) increase your problems?	 Yes  Sometimes  No
E9. Because of your problem, are you afraid to leave your home without having someone accompany you?	 Yes  Sometimes  No
E10. Because of your problem have you been embarrassed in front of others?	 Yes  Sometimes  No
P11. Do quick movements of your head increase your problem?	 Yes  Sometimes  No
F12. Because of your problem, do you avoid heights?	 Yes  Sometimes  No

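### Outcomes are screened for normality on raw values and transformed if skewed, although the mixed model needs normal residuals and random effects, so some may leave their clinical scale without need

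*Protocol*

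**What the plan says.** The opening paragraph of Statistical Analysis in the protocol sets a rule in two steps. The check: "Exploration of central tendency of all data will be evaluated using Kolmogorov-Smirnov and Shapiro-Wilk tests". The action: "Where data is significantly skewed, attempts will be made to transform using suggested methods", with the methods left to reference 57. No separate criterion for skewness is given; the two named tests are the only ones mentioned.

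Under Objective 2 the outcomes go into a mixed model: "Linear mixed method analysis of repeated experimental outcomes will determine treatment effect". Covariates are added: "Effect modifiers including sex and age as well as statistically significant demographic confounders will be included in the final model".

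The table under Experimental Outcomes lists measures in clinical units or on clinical scales, such as degrees, seconds, NDI out of 50 and EQ VAS. The NDI form in Appendix 1 prints "Minimum Detectable Change (90% confidence): 5 points or 10 %points".

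**The concern.** Two things look wrong. First, the label: Kolmogorov-Smirnov and Shapiro-Wilk tests assess whether a sample is compatible with a distributional shape and say nothing about central tendency.

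Second, the target. A linear mixed model assumes approximate normality of the residuals and of the random effects, given visit and covariates. Raw scores also carry differences between participants, differences between visits and covariate effects. They can look non-normal while the residuals are well behaved. A screen on raw values followed by transformation can then move an outcome off its natural scale for a reason that does not threaten the estimate of mean change.

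At stake is the usefulness of the pilot estimates. Study Design says the combined evidence will inform a later pilot randomised trial, and planning that trial is easiest with a mean change and an SD in original units. A change in log or square-root NDI cannot be set directly beside a detectable change given in points. Outcomes that end on different, data-chosen scales are also harder to compare.

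**Working it through.** **Sample size in the plan.** Study power expects 60 eligible from 160 screened. "Allowing for 50% of individuals to decline participation in the trial and a 10% drop-out rate" gives 60 × (1 − 0.50) = 30 starting treatment and 30 × (1 − 0.10) = 27 with complete data. The plan's 27 is reproduced. Visits: screening, 1 week and 3 months after treatment, so three.

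**Number of continuous outcomes.** The Experimental Outcomes table names about 20 non-binary measures: five virtual-reality kinematic measures, flexor endurance time, joint position error, NDI, HIT-6, VOMS symptom rating, near point of convergence, DHI, four actigraphy measures, two PROMIS sleep scores, IPAQ, fatigue severity and EQ VAS. That is 21, or 20 if near point of convergence is used only as above or below its cut-off.

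**Simulation.** The protocol gives no significance level for the distribution tests, so 0.05 is an assumption. The model was outcome = participant effect (SD 1) + visit shift + normal residual, with 27 participants, three visits and 4,000 data sets per scenario (Monte Carlo standard error at most √(0.25/4000) = 0.8 percentage points). Residuals are normal by construction, so a residual check should rarely react. Only Shapiro-Wilk was simulated, not Kolmogorov-Smirnov.

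The trigger can be read in several ways, so four were tried: Shapiro-Wilk significant at any visit; the same with a significant skew test at that visit; Shapiro-Wilk on all 81 values pooled; and pooled with a significant skew test. The last column applies Shapiro-Wilk after removing participant and visit means.

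| Participant effects; residual SD; visit shifts | Any visit | Any visit + skew | Pooled | Pooled + skew | Residual check |
|---|---|---|---|---|---|
| Normal; 1; none | 14.5% | 9.4% | 7.5% | 4.8% | 3.4% |
| Gamma, shape 4; 0.5; 0, −1, −1.2 | 41.0% | 33.8% | 35.2% | 31.8% | 2.7% |
| Exponential; 1; 0, −1, −1.2 | 42.8% | 37.5% | 33.7% | 31.4% | 3.0% |
| Exponential; 0.5; 0, −1, −1.2 | 75.5% | 68.1% | 66.9% | 62.8% | 2.9% |
| Normal; 0.5; 0, −3, −3.5 | 13.3% | 7.7% | 67.8% | 7.2% | 3.0% |

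**Reading the table.**

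- Normal outcomes (first row): about 5% to 15% flagged. Over 20 outcomes, 20 × 0.048 ≈ 1 to 20 × 0.145 ≈ 3.
- Skewed participant levels (rows two to four): about 31% to 76% flagged, with no fault in the residuals.
- Large change over time (last row): pooling the visits makes normal data fail Shapiro-Wilk in 68% of data sets, but only 7% are also significantly skewed. Under the plan's skew trigger this route is small.

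**Was transformation needed?** With exponential participant levels and residual SD 0.5, the ordinary 95% t interval for the untransformed paired mean change (n = 27, 20,000 runs) covered the truth 94.9% of the time. The participant effect cancels in the within-person difference, so its skewness does no harm there.

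**The case against.** Several points on the other side stand.

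- The action is tied to skewness, and the plan promises only attempts. A flag is not the same as a transformation, and nothing says that one flagged visit changes the scale of the whole outcome. The counts above are therefore counts of flags, given as a range over readings of the trigger.
- The paragraph is general. It stands beside the descriptive analyses and the univariate regressions, before the objectives. Looking at raw distributions to choose between mean with SD and median with IQR is legitimate.
- Raw skewness is not irrelevant to the model, because skewed participant levels show in raw scores and the model also assumes normal random effects. The 94.9% coverage answers this for mean change in the one setting tried, not in general.
- Residual diagnostics and back-transformation often sit in a statistical analysis plan, which is not at hand, and the content of reference 57 is not available. Their absence from the protocol is not held against it. The point concerns only the rule that the protocol states.

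Three stronger readings are tempting but not supported. A reader might infer that several needless transformations are certain, for instance by counting 30 outcomes; the table names about 20 continuous ones, and a flag leads only to an attempt. A reader might take the reference to all data to mean that positive/negative items will be tested for normality; the next sentence speaks of skewed data, which makes sense only for continuous variables, so this is loose wording and not a planned analysis. A reader might conclude that the NDI result could no longer be compared with the 5-point figure; nothing prevents reporting untransformed change beside a transformed analysis, and the protocol sets no NDI success criterion on that figure.

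**Conclusion.** The point holds as a minor correction. The protocol mislabels the tests and directs the distributional check at raw data, where the mixed model calls for a check of residuals and random effects. Following the rule can move outcomes off their clinical scale without need; it does not make that certain.

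The likely size is about 1 to 3 flags among roughly 20 continuous outcomes if all are normal. It is larger if participants' levels are skewed, which is plausible for bounded scores such as NDI and DHI and for activity minutes that cannot fall below zero. These figures rest on the assumed 5% level, the assumed distributions, n = 27 at three visits and the reading of the trigger.

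The consequence is limited. The outcomes concerned are exploratory in a single-group feasibility study. The primary feasibility outcomes (completion, adherence, adverse events, satisfaction and the qualitative themes) do not depend on the mixed model.

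**What to change.** Replace the two sentences in Statistical Analysis with wording to this effect:

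- The distribution (in place of central tendency) of continuous variables will be examined, and used only to choose between mean with SD and median with IQR for description.
- Mixed models will be fitted on the original scale by default and judged by plots of residuals and random effects.
- Where residuals are clearly non-normal, a sensitivity analysis, for example bootstrap intervals or a model on a transformed scale, will be reported alongside the mean change and its SD in original units.

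The choice of sensitivity method is open. Bootstrap intervals have their own limits at n = 27, so they should supplement the original-scale result.

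The cost is a change of wording and slightly more analysis work. No data collection, visit or sample size changes.

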- Headache Impact Test – 6 (HIT-6) is a 6-item subjective measure of the impact of headaches, originally based on an existing pool of 54 existing and 35 suggested items [24]. Good internal consistency (Cronbach's $\alpha = 0.89$) and test-re test reliability (0.80) have previously been reported [24]. Sensitivity and Specificity compared to the total HIT scale has been reported at 93.1% and 79.4% respectively [24].

- Fatigue severity scale (FSS) [25] is a 9-item questionnaire measures level of disabling fatigue over the prior week. The scale has demonstrated good levels of internal consistency (Cronbach's $\alpha = 0.89-0.94$) and test-retest reliability (ICC 0.751) in patient populations prone to excessive fatigue.
- PROMIS Sleep Questionnaires [26] are two 8-item questionnaires of Sleep Disturbance (SD) and Sleep-related Impairment (SRI) and demonstrated good construct validity when compared to the longer form [27] as well as other outcome sleep related outcome measures.
- International physical activity questionnaire – Short Form [28] measures physical activity of varying intensities over a 1-week period and has demonstrated high test-retest reliability ($\alpha < 0.8$)
- EuroQol 5 Dimension (EQ-5D-5L) is a 5-dimension measure of health-related quality of life. The EQ-5D-5L provides general measure of quality of life [29]. Specifically, the scale provides information regarding problems within 5 dimensions of health: anxiety/depression, pain/discomfort, mobility, self-care, and usual activities, and a self-rated health value.
- Sociodemographic questionnaire

Ethical considerations for self-report outcome measures:

As participants will be individuals who are acutely concussed it is possible that increased amounts of screen time and reading may result in a temporary increase in symptoms. However, online questionnaires will be constructed so that is possible to log in and out of the online survey tool to allow response over the 24-hours prior to attending the screening session. Further in line with international recommendations outlining resumption of cognitive activities including symptom limited screen time may commence after 24-48 hours of rest post injury [14], participants will not be required to complete questionnaires within this time post injury. This will be clearly indicated at the start of the questionnaire battery and in the participant information sheet.

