Participants identified as eligible for allocation to the treatment arm of the study will be booked for their initial treatment session a maximum of 2 weeks following the screening session. Participants will be assessed during the first treatment session using an extended standardised assessment of the cervical spine (1 hour). Additional tests of musculoskeletal [31, 71] and sensorimotor function [72] as well as neural mechanosensitivity [73], standard to physiotherapy clinical practice in management of disorders of the neck and concussion [74], in addition to baseline results (provided in report form via post from the SC and supplied to the treating physiotherapist) will inform individualised treatment plans [18, 75]. Following initial assessment by the therapist, participants will receive treatment twice weekly for 4 weeks. During this time participants will also be requested to avoid alternate treatments for their concussion (except for use of prescribed medication/s) to minimise potential for confounding.

Interventions:

Treatment for management of identified neck impairments provided will include OMT (For e.g., Maitland, and Mulligan intervertebral joint mobilisation techniques) neuromuscular and sensorimotor retraining techniques standard to musculoskeletal physiotherapy practice internationally and in New Zealand for management of neck disorders [18, 75]. Individual treatment plans will be pragmatically determined. All participants receiving treatment will be provided with advice and education relating to graduated return to activity and prescribed a sub-symptom threshold cardiovascular exercise program using previously published

guidelines for exercise intensity dose [76]. This adjunct treatment aligns with internationally accepted standards of best practice for concussion management [4].

Treating physiotherapists, up-skilling, and treatment monitoring:

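### BMI and IPAQ enter the experimental models through a significance screen at about 27 patients, IPAQ is treated as a demographic although it is an outcome, and time since injury is not named

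*Protocol*

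**What the plan says.** All references are to the protocol; no statistical analysis plan was available.

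- **Statistical Analysis, opening paragraph.** The candidates are "Individual demographic variables (sex, age, BMI, IPAQ score) which could reasonably be expected to influence quantitative outcomes", and they "will be analysed for significance using univariate linear regression and included in models".
- **Statistical Analysis, Objective 2.** For the linear mixed analysis of the repeated experimental outcomes: "Effect modifiers including sex and age as well as statistically significant demographic confounders will be included in the final model".
- **Inclusion criteria.** Participants "are not more than 14 days since injury".
- **Treatment sessions procedure.** Eligible participants are "booked for their initial treatment session a maximum of 2 weeks following the screening session", and then "participants will receive treatment twice weekly for 4 weeks".
- **Follow up sessions.** Visits fall 1 week and 3 months after treatment ends, with the same questionnaire battery each time.
- **Questionnaires.** IPAQ "measures physical activity of varying intensities over a 1-week period". The battery is completed 1 day before the screening session.
- **Experimental Outcomes table.** IPAQ is listed there as an outcome, as are the actigraphy measures.
- **Study power.** 30 participants start treatment and 27 are expected to have data at all time points.

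Time since injury is not named in the analysis text.

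**The concern.** There are three weaknesses in one short covariate rule.

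First, the opening paragraph tests all four variables, while Objective 2 enters sex and age by name and applies significance only to the rest. Whoever writes the code must choose between them. Whichever reading is taken, BMI and IPAQ depend on a p-value from a sample of about 27, so the model for neck disability may differ from the model for headache impact for no reason other than noise.

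Second, IPAQ is not a demographic. For a participant screened on day 12 and completing the form on day 11, the recalled week lies wholly after the injury. For one screened on day 3 and completing it on day 2, about 5 of the 7 days lie before it. The covariate's meaning therefore shifts with time since injury. The protocol does not say which IPAQ score is used, nor that IPAQ is left out of the models in which activity is the outcome.

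Third, follow-up is timed from the end of treatment, so one nominal visit falls at quite different times after injury, and nothing in the stated model accounts for this.

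At stake is the quality of the preliminary estimates that are meant to inform a later controlled trial (Study Design).

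**Working it through.** **1. Sample size, reproduced.** 60 eligible × (1 − 0.50) = 30 starting; 30 × (1 − 0.10) = 27. Both match Study power.

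**2. Timing windows.** Inputs: injury to screening 0–14 days; screening to first treatment 0–14 days; treatment 28 days; first follow-up 7 days later; 3 months taken as about 91 days.

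| Point | Days since injury | Spread |
|---|---|---|
| Screening | 0 to 14 | 14 |
| First treatment | 0+0 to 14+14 = 0 to 28 | 28 |
| First follow-up | 0+0+28+7 to 14+14+28+7 = 35 to 63 | 28 |
| 3-month visit | 0+0+28+91 to 14+14+28+91 = 119 to 147 | 28 |

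The interval from screening to first follow-up is (0 to 14) + 28 + 7 = 35 to 49 days, a spread of 14.

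The lower limits are generous. After the 24–48 hour rest period is described, the protocol says that "participants will not be required to complete questionnaires within this time post injury". With a floor of 1–2 days, the spreads become 12–13 days at screening and 26–27 from first treatment on. In the other direction, the text sets no maximum delay between first contact and the screening session. If the 14-day limit is applied at contact, the spread at screening could exceed 14.

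**3. What the screen does at n=27.** The protocol states no alpha; two-sided 0.05 is assumed. The true correlations are also assumptions, shown as a range.

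- Smallest observed correlation that passes: t/√(n−2+t²) with t = 2.06 on 25 df, which is 2.06/√(25+4.24) = 0.38.
- Chance of passing by the Fisher z approximation: 1 − Φ(1.96 − atanh(r)·√24), plus a negligible lower tail. For r = 0.3, atanh(0.3) × 4.90 = 1.52, so 1 − Φ(0.44) = 0.33.

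| True r | Kept at n=27 | Kept at n=30 |
|---|---|---|
| 0.2 | 17% | 18% |
| 0.3 | 33% | 36% |
| 0.4 | 55% | 60% |

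- Simulation of 200,000 samples of 27 gave the same picture (17% and 34% for r = 0.2 and 0.3). When the covariate was kept, its slope was inflated about 2.3-fold and 1.6-fold.
- Chance that at least one irrelevant covariate is kept, per outcome, if independent: 1 − 0.95² = 9.8% with two screened (BMI, IPAQ); 1 − 0.95⁴ = 18.5% with four.

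**4. What a timing covariate can and cannot do.** Time since injury is constant within a person. In a mixed model with a random intercept and complete data, its main effect explains differences between people and leaves the visit effect and its SE unchanged. Only an interaction with visit acts on the change. For a single pre-post change, this is the same as regressing the change on centred timing: the estimated mean change is identical, and its SE falls from √(σ² + β²V)/√n to σ/√n, apart from degrees of freedom.

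Illustration with assumed values: timing uniform from day 2 to 28, so V = 26²/12 = 56.3; residual SD σ = 3; n = 27.

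| Assumed slope β per day | SE without | SE with | Reduction |
|---|---|---|---|
| 0.05 | √(9+0.14)/5.196 = 0.58 | 0.58 | about 1% |
| 0.15 | √(9+1.27)/5.196 = 0.62 | 0.58 | about 6% |
| 0.30 | √(9+5.07)/5.196 = 0.72 | 0.58 | about 20% |

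Simulation of the middle row gave 0.61 and 0.57, with the same mean change to machine precision.

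**5. IPAQ by visit.** If an outcome changes by Δ on average, IPAQ changes by d, and the model slope on IPAQ is b, then the visit coefficient after adjusting for visit-specific IPAQ is approximately Δ − b·d. All treated participants are prescribed cardiovascular exercise (Interventions), so d can itself be a result of the programme, and b·d is part of the change being studied.

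**The case against.** The case on the other side is substantial, and much of it stands.

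- **A reader might infer that all four covariates are chosen by significance.** Objective 2 does not support that: sex and age enter by name. What remains is a conflict between two paragraphs and a filter on BMI and IPAQ.
- **A reader might take the 28-day spread to apply to the baseline data.** It does not. At screening the windows give at most about 14 days; 28 is approached only from first treatment onward.
- **The covariate list is open.** Objective 2 introduces sex and age with the word including, and a statistical analysis plan could add days since injury. That is fair, so the omission alone would be a weak point. But the significance rule and the labelling of IPAQ are stated in the protocol itself, and correcting them is the natural moment to name timing.
- **Adjustment for follow-up IPAQ is proposed nowhere.** Correct. Grouping IPAQ with demographics suggests one baseline value. The text does not say so, however, and IPAQ is collected at every assessment.
- **The choice of timing is a judgement.** The Background names acute symptom load as the strongest predictor of persistent symptoms and makes no comparable statement about time since injury. The argument for timing rests on the protocol's own unequal windows.
- **Little depends on it.** The primary outcomes are feasibility outcomes, and no feasibility threshold uses these models. This stands and limits the weight of the point.

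**Conclusion.** The point holds in a limited form. The protocol states two covariate rules that disagree on sex and age. It applies to BMI and IPAQ a significance screen that, at n=27 and an assumed 5% level, keeps a covariate with true r = 0.3 only about one time in three. It classes as a demographic a questionnaire that is also a repeated outcome. It names no timing term, although time since injury can differ by up to about 14 days at screening and about 28 days (slightly less in practice) at first treatment and follow-up.

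Two stronger conclusions should not be drawn. Nothing here shows that the mean change is biased by leaving timing out: with complete data, a centred timing term leaves the estimate where it was, and adding one would not separate treatment from natural recovery without a control group. Nor has it been shown that the confidence intervals are too narrow; the calculations concern how often the screen keeps or drops covariates, not interval coverage.

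The consequence is less precise and less comparable exploratory estimates. How much precision is lost depends on how steeply change varies with time since injury, which the protocol does not give; the assumed range above runs from about 1% to 20% of the SE.

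**What to change.** In Statistical Analysis:

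1. Delete the univariate significance screen and make the opening paragraph and Objective 2 state the same rule.
2. Use one fixed covariate set for every experimental outcome: visit, age, sex, centred days from injury to screening, and centred days from screening to first treatment. Enter the two timing variables as interactions with visit, because main effects alone change neither the mean change nor its SE.
3. Do not use IPAQ as a covariate. If it is kept, use only the screening value, and never in the models for IPAQ or actigraphy.
4. State that the timing terms serve precision and description, and are not an adjustment for natural recovery.

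The cost is analysis wording and a few degrees of freedom at n=27. Injury timing is already an eligibility item, and the date of the first session should be available from the treating physiotherapist's treatment records. No visit, measurement or treatment procedure changes.
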